The double-sided arrows represent 95% confidence intervals for the model-estimated adjusted mean 24-week difference in QIDS-SR16 score. Note that higher score signifies more depressive symptoms; thus if the estimated difference (HV minus MH score) is larger than zero, the HV arm has on average worse depressive symptoms. Since the pre-specified margin of non-inferiority is two units on the QIDS-SR16 scale, we will claim non-inferiority if the upper limit of the adjusted 95% confidence interval for the HV-led arm minus the MH-led arm comparison remains below two. The red arrows indicate scenarios in which we cannot claim non-inferiority and the blue arrows indicate scenarios in which the criterion for non-inferiority is met.

Using the same analytic approach, we will explore the addition of covariate-by-arm interaction terms in the aforementioned model or a three-way covariate-by-arm-by-time interaction term in the longitudinal modelling in order to explore whether effectiveness of intervention varies by patient characteristics (Aim #3). The covariates to be explored include: race/ethnicity, first-time mother, language, education, and use of mental health services at baseline. These analyses are more exploratory in nature, and thus power/sample size considerations do not focus on interaction effects. As a result, we anticipate evaluating interaction effects at the 10% level of significance without adjustment for multiple hypothesis tests. Qualitative data analysis methods will evaluate feasibility and acceptability of MB in each setting (Aim #4), and the details of these analyses will be specified elsewhere.

Additional analyses surrounding Aims #1-#3 will employ longitudinal methods, utilizing all study data at all time points (i.e., inclusion of a fixed study time point effect). Secondary outcomes will all be analyzed in this fashion with the exception being binary response variables (e.g., depression onset). In these cases, appropriate link and distributional assumptions (logit, binomial, respectively) will be specified. For the participants receiving active intervention (either HV-led or MH-led Mothers and Babies), we will examine a 'dose' variable in relation to outcomes. This dose variable will be defined as the number of sessions (out of six possible) attended for an individual participant.

Analytic Dataset

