Analyses will be conducted on the modified intent-to-treat (mITT) dataset whereby all participants randomized with data at the 24-week time point will be analyzed according to arm to which they were allocated. We will further perform a sensitivity analysis on the 'as treated' dataset. Those in either active intervention arm will be considered 'treated' if they attend at least four out of the six sessions required for the Mothers and Babies course. For participants with missing data at baseline and non-missing data at follow-up, we plan to impute mean baseline values from the participants' follow-up in order to allow for inclusion in analyses.

Power and sample size considerations allowed for some missing data and, as specified in our approved research plan, we have allowed for up to two clusters to drop out of each arm; however, in the event of large amounts of missing data (i.e., more than 15%), multiple imputation analyses will be explored. We will examine rates of missing data for all variables and determine whether the rates vary by participant characteristics, HV program location, or intervention arm. These summarizations will inform potential biases resulting from missing data. The mixed effects models planned for analysis are generally robust for unbalanced data across study time points. We plan to apply multiple imputation in order to account for missing data; we will impute at least five datasets to generate an estimated average intervention effect. These analyses will again serve as sensitivity analyses to the previously outlined analyses. For participants missing individual items on a particular assessment, we plan to randomly sample from the non-missing empirical distribution for that item. We anticipate less than 5% of participants that would require this imputation of individual items. Again, in the event of large amounts of missing individual items, we will explore multiple imputation methods.

Power and Sample Size Considerations

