We initially planned to conservatively enroll 42 sites (six controls, 18 HV-led, 18 MH-led) with a target enrollment of 40 participants per site (1680 total participants). As in any cluster-randomized trial, power and sample size considerations depend heavily on intra-cluster correlation coefficient (ICC) estimates. In general, it is recommended that these calculations account for anticipated ICC as failure to do so in the design phase and lead to an increase in type II error (i.e., result in underpowered studies) [4, 5]. Without previous knowledge of ICC(s) in this population with respect to our primary outcome, we explored a range of ICCs (0.001 to 0.05). Power calculations assume a standard deviation in primary outcome of approximately six points (on the QIDS-SR16), with a meaningful difference corresponding to five points on average across arms. Thus, for the superiority aim, we calculated power based on the average ability to detect at least a five-point mean difference between control sites and HV-led sites. Power calculations assumed a $5\%/3 = 1.7\%$ level of significance in order to account for three pairwise comparisons. This is an approach that we deem conservative as this mirrors the Bonferroni correction for multiple hypothesis tests.

We have 38 active sites: six control, 16 paraprofessional home visitor-led sites, and 16 MHP-led sites. We plan to recruit an average of 27 participants per site, allowing for up to 15% attrition (i.e., 23 participants on average for analyses). These assumptions allow for more than 95% power to detect a mean difference of five points in QIDS-SR16 across arms for an ICC of 0.01. Even if one of the six sites drops out, and if ICC is as large as 0.05 (which we deem unlikely), we still anticipate over 85% power for analyses addressing the efficacy aim (Aim #1).

Power for the NI aim will require ability to detect a smaller (margin of NI of two points) mean difference across arms. We anticipate over 90% power to detect a margin of NI of two points on the QIDS-SR16 scale if we assume an ICC of 0.01 and 16 sites in each of the intervention arms with 23 participants for analyses, on average, per site. This allows for up to 15% attrition overall. We anticipate some sites to be over/underperforming and thus unequal representation per site is inevitable. Our hope is that the precautions taken with respect to the randomization algorithm that

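### The as-treated sensitivity analysis sorts Mothers and Babies (MB) women by attendance after randomisation, with no counterpart in control, so its HV v control comparison is not randomised; a complier-average estimate would be a better check

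*SAP*

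**What the plan says.** The main analysis set in the SAP (Analytic Dataset) is mITT: "all participants randomized with data at the 24-week time point will be analyzed according to arm to which they were allocated". The next sentence adds the adherence check: "We will further perform a sensitivity analysis on the 'as treated' dataset". Women in either MB arm are then treated "if they attend at least four out of the six sessions required for the Mothers and Babies course".

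No criterion is given for control. The section does not say whether MB women below four sessions are dropped or counted with control, which pairwise comparison the analysis serves, or how selection on attendance is handled beyond the model covariates.

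Two other items concern attendance. Under Statistical Methods the SAP plans to relate dose to outcome within the MB arms: "This dose variable will be defined as the number of sessions (out of six possible) attended for an individual participant". Under Study Outcomes it plans to summarise sessions attended and the number of women reaching four of six.

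The non-inferiority rule concerns HV minus MH only. The claim is made if the "upper limit of the adjusted 95% confidence interval for the HV-led arm minus the MH-led arm comparison remains below two". The superiority comparison, HV v control, is powered on a five-point difference (SAP, Power and Sample Size Considerations).

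**The concern.** Women who come to four or more sessions are unlikely to be a random subset of those allocated to MB. The protocol cites childcare, transport and stigma as barriers to using services (Background) and describes many participants as transient (Recruitment). It lists stressful life events, poor social support and low socioeconomic status as risk factors for postpartum depression (Inclusion and exclusion criteria). Factors of this kind can affect both attendance and the 24-week score. The model adjusts for baseline QIDS-SR16, depressive-episode status, education, counselling and medication, but not for social support, stress or income, so adjustment may be incomplete.

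Control women cannot be sorted in the same way. The analysis therefore compares selected HV women either with all controls or with controls plus the HV (and perhaps MH) women who stayed away. Either way the groups can differ in prognosis with no treatment effect at all. A check built like this can seem to corroborate the main result, or to contradict it, because of who attended. Leaving the handling of non-attenders open also leaves a choice to be made after the data are seen.

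**Working it through.** **Anchor to the plan.** The documents give no figure for this bias, so none can be reproduced. The SD can be checked against the plan's own power figures. Take SD 6, a 2-point difference, two-sided alpha 0.017, variance 6² × (1 + (m − 1) × ICC)/(k × m) per arm for k sites of m women, and a noncentral t with 2(k − 1) degrees of freedom. All 12 cells of SAP Table 1 for analysed women per site are reproduced (16 sites: 17, 20, 25, 33, 49, 97; 15 sites: 19, 22, 28, 38, 62, 168). Power with 16 sites of 23 per arm at ICC 0.01 is about 93%, consistent with the stated figure of over 90%.

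**Inputs from the SAP.**
- SD 6 and 23 analysed women per site (Power and Sample Size Considerations).
- 6 control, 15 HV and 16 MH sites contributing data (Randomization Methods). This gives 6 × 23 = 138 control, 15 × 23 = 345 HV and 16 × 23 = 368 MH women. The power section counts 16 active HV sites; 15 is used here.

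**Inputs assumed, because neither document gives them.**
- p, the share attending at least four sessions: 50-60%.
- r, the correlation between attendance propensity and better 24-week outcome without treatment: 0.1-0.3. If more symptomatic women attend more, every sign below reverses.

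**Formulas (true effect zero, normal selection).** With z the normal quantile of p and φ the normal density:
- attenders score lower than their whole arm by A = 6 × r × φ(z)/p;
- non-attenders score higher by N = 6 × r × φ(z)/(1 − p).

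At p = 0.5, φ = 0.3989, so A = 4.79r and N = 4.79r. At p = 0.6, φ = 0.3863, so A = 3.86r and N = 5.80r.

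**HV v control, non-attenders dropped.** The false difference is A.
- p = 0.5: 0.48 (r = 0.1) to 1.44 (r = 0.3).
- p = 0.6: 0.39 to 1.16.

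**HV non-attenders moved to control.** The control pool rises by N × n/(n + 138), where n = 345 × (1 − p).
- p = 0.5: n = 172.5; total 4.79r + 4.79r × 172.5/310.5 = 7.45r, or 0.74 to 2.23.
- p = 0.6: n = 138; total 3.86r + 5.80r × 138/276 = 6.76r, or 0.68 to 2.03.

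**MH non-attenders moved as well.** Now n = (345 + 368) × (1 − p).
- p = 0.5: n = 356.5; total 4.79r + 4.79r × 356.5/494.5 = 8.24r, or 0.82 to 2.47.
- p = 0.6: n = 285.2; total 3.86r + 5.80r × 285.2/423.2 = 7.77r, or 0.78 to 2.33.

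**Effect of baseline adjustment.** If the covariates cut the residual SD to 5.2 (assumed), the dropped-version range scales by 5.2/6 to about 0.33-1.24. Adjustment may also lower r.

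**HV v MH, the same rule in both arms.** The bias is the difference between two values of A.
- Equal attendance and equal r: 0.
- 50% v 70%: (4.79 − 2.98)r = 1.81r, or 0.18 to 0.54.
- 40% v 70%: (5.80 − 2.98)r = 2.81r, or 0.28 to 0.84. Reaching 2 points would need r = 0.71.
- 50% in both arms but selection in one arm only: 0.96 at r = 0.2, 1.44 at r = 0.3, 1.91 at r = 0.4.

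**The case against.** The strongest reply is that this is a labelled sensitivity analysis. Superiority and non-inferiority are both decided on mITT by allocated arm, so the as-treated result cannot change either claim. That stands, and it limits the point to an improvement.

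An adherence-based comparison also has a purpose in a non-inferiority setting, where poor attendance can pull mITT towards no difference. That stands too, and is a reason to keep an HV v MH attender comparison in a supportive role.

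The size rests on an assumed attendance rate and correlation, on a raw SD where the model would use a residual one, and on an assumed direction. This is fair: the figures show what could happen, not what is expected.

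A reader might infer from the 0.7-2.2 range that the as-treated set can generate a false difference about as large as the non-inferiority margin. The documents do not support that. The SAP states that "the pre-specified margin of non-inferiority is two units on the QIDS-SR16 scale", but the margin is for HV minus MH, where one attendance rule filters both arms. The larger figures belong to HV v control, whose benchmark is 5 points. Only strong selection in one arm alone brings HV v MH near 2.

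A reader might also infer that this is the plan's only look at non-attendance. It is not: the dose analysis within the MB arms is another. That analysis also relies on self-selected attendance, so it does not repair the problem.

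**Conclusion.** The concern holds as a point about one sensitivity analysis. Classifying MB women by attendance, with nothing equivalent in control, makes the as-treated HV v control comparison non-randomised, and the handling of women below four sessions is undefined. Under the stated assumptions (no true effect, SD 6, 50-60% attendance, r of 0.1-0.3) the false difference is about 0.4-1.4 points with non-attenders dropped, 0.7-2.2 with HV non-attenders moved, and 0.8-2.5 with MH non-attenders moved too. Baseline adjustment would reduce these, and the sign depends on who attends. For HV v MH the bias is about 0 to 0.8 points for attendance gaps up to 30 percentage points, unless selection itself differs between arms. The primary superiority and non-inferiority conclusions are not affected.

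**What to change.** For HV v control, make the adherence sensitivity analysis a complier-average estimate with allocated arm as the instrument. Keep all women in the mITT set for these two arms, and account for site clustering. Run it with sessions attended (0 to 6) as the dose, and again with uptake defined as four or more sessions. State the assumptions:

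- Both versions: allocation affects outcome only through attendance.
- Threshold version: one to three sessions have no effect, which is doubtful for a six-session skills course.
- Dose version: the effect is linear per session.

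If allocation has no effect, this estimate is centred on zero whoever attends, apart from any selection already introduced by requiring 24-week data.

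Keep any HV v MH attender comparison only as a supportive, non-randomised analysis. Say in advance how women below four sessions are handled, report attendance by arm beside it, and do not cite it as confirming non-inferiority.

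The attendance forms and the follow-up regardless of attendance are already in the protocol (Procedures Involved), so no new data are needed. The cost is a little more analysis work and wider intervals: treating uptake as known, the threshold version's standard error is the allocated-arm one divided by uptake, so about 1/0.5 = 2 times as wide at 50% and 1/0.6 = 1.7 times at 60%.

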Analyses will proceed at the participant level. Primary analyses for QIDS-SR16 score at 24 weeks postpartum will involve all the participants in the study contributing data at this time point. Primary analyses will involve a linear mixed model for continuous outcome with independent fixed effect variables of baseline QIDS-SR16, study arm (three-level factor), and the baseline covariates listed above. We will report both covariate-adjusted and unadjusted estimates for intervention effect. Secondary analysis will be performed on those participants considered at risk at baseline (i.e., excluding the participants who do not meet the criteria for MDE as defined above). We plan to account for clustering effects via inclusion of a random site effect, which will allow for distinction of between and within-site variance. We will also explore inclusion of a random 'facilitator' effect as it is possible participants exposed to the same facilitator may have correlated responses. Intra-cluster correlation coefficients will be estimated via variance components estimates.

Intervention effect will first be evaluated via the adjusted Wald type III test for significant study arm effect at the 5% level of significance. If arm is significant at the 5% level, analyses evaluating the **superiority (Aim #1)** of HV-led intervention vs. control will proceed with Tukey's correction for multiple pairwise hypothesis tests. Assuming the Tukey-adjusted p-value for this comparison falls below the 5% level of significance in favor of the HV-led arm, **non-inferiority (Aim #2)** will further be assessed (using Tukey's correction) via pairwise comparison of adjusted 24-month QIDS in HV-led vs. MH-led arms. Figure 1 below depicts the margin and zone of non-inferiority for this comparison.

[figure not shown]

Figure 1. Margin of Non-inferiority (NI)

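### A missing baseline QIDS-SR16 would apparently be filled from the woman's own follow-up and then used as a covariate in the model that decides non-inferiority

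*SAP*

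**What the plan says.** The SAP (Analytic Dataset) analyses all randomised women who have 24-week data. For those without a baseline it says: "For participants with missing data at baseline and non-missing data at follow-up, we plan to impute mean baseline values from the participants' follow-up". It does not say whose mean is meant or which visits supply it, and it does not exempt QIDS-SR16.

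The primary model (SAP, Statistical Methods) is a linear mixed model for 24-week QIDS-SR16 with a random site effect and "independent fixed effect variables of baseline QIDS-SR16, study arm (three-level factor), and the baseline covariates listed above". Non-inferiority is tested after an overall arm test and a superiority test, with Tukey's correction, and the rule is: "we will claim non-inferiority if the upper limit of the adjusted 95% confidence interval for the HV-led arm minus the MH-led arm comparison" stays below 2 points.

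Three related safeguards are planned:
- **Unadjusted estimate:** "We will report both covariate-adjusted and unadjusted estimates for intervention effect".
- **Missingness:** rates will be examined to "determine whether the rates vary by participant characteristics, HV program location, or intervention arm".
- **Multiple imputation:** "These analyses will again serve as sensitivity analyses to the previously outlined analyses".

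On the second point, item 4 of Demographics and Baseline Assessments takes language from the sessions received in the MH and HV arms, but from the assessments in control.

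**The concern.** A baseline covariate should carry nothing that the intervention could have changed. If a follow-up score stands in for a missing baseline, part of the arm effect moves into the covariate and the model adjusts it away. If the fill is the 24-week score, those women's outcomes are regressed partly on themselves.

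The interval that decides non-inferiority comes from this model, and the margin is only 2 points. The planned safeguards may reveal a distortion, but none of them alters the decision rule.

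The language covariate has a related weakness. It measures one thing in the MB arms and another in control, and it has no value for a woman in an MB arm who attended no session. SAP, Randomization Methods counts 16 + 15 = 31 MB sites contributing data, of which 29 ran a cohort. So 31 − 29 = 2 sites have no sessions from which to take a language.

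**Working it through.** **Plan's own figure.** The SAP states over 90% non-inferiority power with margin 2, SD 6, ICC 0.01, and 16 sites per arm with 23 women analysed per site. The variance per arm is 36 × (1 + 22 × 0.01)/(16 × 23) = 0.119, so the SE of the difference is √(2 × 0.119) = 0.489. At two-sided 1.7% with 2 × (16 − 1) = 30 df, power is 0.93. The same method reproduces all 12 analysed-per-site entries in SAP Table 1. The power figures are not in dispute.

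**Inputs for the check.** SD 6, ICC 0.01, 23 women per site and the 2-point margin come from the SAP. So do the 15 HV, 16 MH and 6 control sites (Randomization Methods; the power section counts 16 HV). Assumed, because the documents do not give them: baseline-outcome correlation r = 0.5 (range 0.3 to 0.7), missing proportion p, missingness random within arm, and fill by the 24-week score.

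**Equal missingness.** Let D be the true difference. The filled covariate differs between arms by p × D. Its within-arm slope is b = r + p(1 − r), because a fraction p of women have the outcome on both sides. Hence

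adjusted estimate = D × [1 − p × (r + p(1 − r))].

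At p = 0.10 this is 2 × [1 − 0.10 × 0.55] = 1.89. A simulation of the three-arm mixed model (24,000 replicates per scenario) agrees. The false non-inferiority range reflects Tukey multipliers from 2.45 (34 df) to 2.34 (large df):

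| Missing | HV-MH estimate (true 2.0) | False non-inferiority |
|---|---|---|
| 0% | 2.00 | 0.8–1.1% |
| 2% | 1.98 | 0.9–1.2% |
| 5% | 1.95 | 1.1–1.5% |
| 10% | 1.89 | 1.6–2.1% |
| 12% | 1.87 | 1.8–2.4% |
| 15% | 1.83 | 2.2–2.8% |
| 20% | 1.77 | 3.2–4.0% |

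Applying the overall and superiority gates first left these rates unchanged to two decimals. At 10% missing, r = 0.3 gives 1.93 and 1.2–1.6%, and r = 0.7 gives 1.86 and 2.4–3.0%. Filling with the mean of three follow-ups gives 1.88 at 10%. A true HV-control effect of −5 becomes −4.87, −4.73 and −4.41 at 5%, 10% and 20% missing.

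**Unequal missingness.** With mean change Δ from baseline in each arm, the estimate is about D − b × (p_HV × Δ_HV − p_MH × Δ_MH). Assume HV improves by 2 points and MH by 4, so D = 2:
- HV 5%, MH 15%: 2 − 0.55 × (−0.10 + 0.60) = 1.73 (simulated 1.73; false non-inferiority 3.8–4.7%).
- HV 15%, MH 5%: 2 − 0.55 × (−0.30 + 0.20) = 2.06 (simulated 2.05; 0.6–0.8%).
- HV 2%, MH 6%: simulated 1.90 (1.6–2.0%).
- HV 6%, MH 2%: simulated 2.02 (0.7–1.0%).

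If the arms are truly equal and both improve by 2 points, a 5% v 15% split shifts the estimate by 0.55 × 0.20 = 0.11, in a direction set by which arm misses more.

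**Does the repair work?** Filling with the observed baseline mean pooled over arms, plus a missing indicator, gives 2.00 and 0.8–1.1% at 10% missing. It is not proof against every mechanism. Large-sample regressions with about 12% missing, truth 2.0, and missingness driven in opposite directions in the two arms gave:

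| Missingness depends on | Own follow-up | Pooled fill | Multiple imputation | Observed baseline only | Unadjusted |
|---|---|---|---|---|---|
| Baseline severity | 2.11 | 2.44 | 2.38 | 2.00 | 2.00 |
| Same, direction reversed | 1.63 | 1.58 | 1.63 | 2.00 | 2.00 |
| Unmeasured prognosis | 1.58 | 2.00 | not run | 1.41 | 2.00 |

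**The case against.** The strongest reply is that this hardly matters at plausible rates. Protocol 8.0 takes consent at the first web survey, and Protocol 4.0 has non-completers phoned before the first group, so a wholly missing baseline should be rare. At 5% missing the bias is 0.05 points against a standard error of roughly 0.35 to 0.48. Tukey's interval is already stricter than a plain 95% interval. The worst error rates need a gap between arms that nothing in the documents suggests. All this stands, and it is why the distortion is called probably small.

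A second reply is that the sentence may mean the average of other women's observed baselines. If so, the carry-over disappears. The sentence would still need rewording, because two analysts could build different primary datasets from it.

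A third is that the replacement is not uniformly better. This is true: in both directions of severity-dependent missingness, pooled fill does slightly or clearly worse than the current rule, and one of those directions favours false non-inferiority. Restricting to women with an observed baseline also fails when missingness follows unmeasured prognosis. No single fill is safe, so the analyses need to be read together. The case for keeping follow-up data out of the covariate does not depend on which baseline-only fill is chosen.

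On language, control women attend no MB sessions, so some substitute was unavoidable. The definition is common to HV and MH, so the mismatch does not affect their contrast in Aims 2 and 3.

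**Conclusion.** The concern holds. On its natural reading the SAP puts post-randomisation data into the baseline covariate of the model that decides Aims 1 and 2. The planned unadjusted and multiple-imputation results do not enter the non-inferiority rule.

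With equal missingness the bias is toward zero, which is conservative for superiority. At r = 0.5, false non-inferiority rises from 0.8–1.1% with none missing but reaches 2.5% only near 15% missing. That is the level at which the SAP says: "in the event of large amounts of missing data (i.e., more than 15%), multiple imputation analyses will be explored". At r = 0.7 it reaches that level at about 10%. With unequal missingness and a mean change over time, the direction depends on which arm misses more.

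These sizes rest on the assumed correlation, missing rates and mechanism, none of which the documents give. Confidence is medium, and the rule should be corrected before analysis. The language point is minor: it bears only on comparisons with control, no direction of bias is shown, and the number of women at the two sites without a cohort is not stated.

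**What to change.** In SAP, Analytic Dataset:
- State that missing baseline values are filled from observed baseline data only, using neither arm nor follow-up. One option is the observed baseline mean pooled over arms, with a missing-baseline indicator in the model.
- Report the number filled in each arm.
- Keep multiple imputation as a sensitivity analysis, add an analysis in women with an observed baseline, and show both beside the unadjusted estimate.
- Say that non-inferiority will be described as sensitive to missing baselines if these analyses disagree on whether the upper limit is below 2. Acknowledge that each check has its own weakness, as shown above.

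In Demographics and Baseline Assessments, item 4, define language in all three arms by the baseline assessment, or the first completed one. Every woman in the analysis set has 24-week data, and Protocol 8.0 provides assessments in English or Spanish, so the value exists for each.

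The cost is a few sentences of SAP text and one extra model run, with no new data.
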